### 10.1.4 ADCS-Clinical Global Impression of Change (CGIC)

The Alzheimer's Disease Cooperative Study – Clinical Global Impression of Change (ADCS-CGIC) was developed by the Alzheimer's Disease Cooperative study (ADCS) (Schneider et al., 1997). The ADCS-CGIC is a validated categorical measure of change in the patient's clinical condition between baseline and follow-up visits. It measures whether the effects of active treatment are substantial enough to be detected by a skilled and experienced clinician on the basis of a clinical interview and examination. The 7 responses and corresponding numeric scores for each response of the ADCS-CGIC are: Marked improvement (1), Moderate improvement (2), Minimal improvement (3), No change (4), Minimal worsening (5), Moderate worsening (6), Marked worsening (7). The observed scores at each visit will be summarized. A responder is defined as a subject who responded as “Marked improvement, Moderate improvement, Minimal improvement, No change” and non-responder is defined as a subject who responded as “Minimal worsening, Moderate worsening, Marked worsening”.

### 10.1.5 ADCS-Activities of Daily Living (ADCS-ADL)

The ADCS-ADL (Galasko et al., 1997) is a 23-item informant-administered assessment of functional impairment in terms of activities of daily living. Informants respond to 23 questions about the patient's involvement and level of performance across items representing daily living. The questions range from basic to instrumental activities of daily living. Each item is rated from the highest level of independent performance to complete loss. Each response has a point value, and the total score is the summation of the numeric values. The total score range is from 0- 78 with lower scores indicating greater functional impairment. Total score is obtained directly from CRF.

### 10.1.6 Movement Disorder Society – United Parkinson's Disease Rating Scale Part III (MDS-UPDRS Part III)

The MDS-UPDRS3 is a gold standard assessment of the motor examination of parkinsonism (Goetz et al., 2008), a core feature of DLB (McKeith et al., 2017). The motor exam covers 18 motor signs associated with parkinsonism covering bradykinesia, rigidity, tremor, and gait with a range of scores from 0-136, with higher scores supporting more severe symptoms. A score of 6

or greater suggest the presence of parkinsonism (Goetz et al., 2008). Total score is obtained directly from CRF.

### 10.1.7 Cognitive Drug Research Battery (CDR)

The CDR System is an automated test system designed to precisely measure and profile such patterns of changes to cognition. The CDR System has been specifically developed to assess both enhancement and impairment of human cognitive function. The assessment procedures developed for the CDR System definitively measure changes in the following major areas of cognitive function: Attention, vigilance and information processing; Working memory; Verbal and non-verbal episodic secondary memory; and Executive function. The composite scores for each cognitive function will be calculated and provided from the data vendor (Signant Health) following the derivations provided in Appendix D.

### 10.1.8 Neuropsychiatric Inventory (NPI)

The NPI assesses common behaviors associated with dementia. A structured interview of the caregiver is used to assess 12 behavior domains. For each item within a domain, the symptom frequency is rated as: 1, occasionally; 2, often; 3, frequently; 4, very frequently and the symptom severity is rated as: 1, mild; 2, moderate; 3, marked. The total domain score is calculated as the sum of the frequency scores multiplied by the severity scores for each item assessed within a domain and is obtained directly from CRF. The total NPI score is obtained by adding the domain scores for each of the 12 domains, and ranges from 0 to 144 (144 is the worst possible score). The higher the total score, the more severe the symptoms. Additionally, a caregiver distress score is recorded for each behavior domain ("How emotionally distressing do you find this behavior?") and is rated on a 0- to 5-point scale where 0 is 'Not at all' and 5 is 'Very severely or extremely'. The total caregiver distress score is calculated as the sum of the individual caregiver distress scores recorded for the 12 behavior domains and ranges from 0 to 60. The total score and total distress score are both collected from two separate fields in CRF: Total Score A-J, Total Score A-L, Total Distress Score A-J, Total Distress Score A-L.

## 10.2 Baseline Values

Unless otherwise noted, baseline is defined as the last non missing value recorded before or on the date of first dose of study drug. Unscheduled visits will be used in the determination of baseline values, when applicable.

For all efficacy assessments, baseline will be considered as the latest assessment conducted within 6 hours after the first dose of study drug.

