3.3 Clinical Experience

CT1812 has been administered safely with good tolerability in over 60 healthy volunteers in a placebo-controlled Phase 1a trial (COG0101). Six single (10-1120 mg) and three multiple dose cohorts (QD, 14 days, 280-840 mg) were observed under close inpatient stay (N=6-8 treated, 2 placebo per cohort). Plasma concentrations of drug were shown to be approximately dose proportional across two orders of magnitude [0.13-14.93 mg (free base equivalent)/kg], and accumulation was minimal. Peak concentrations of CT1812 were reached within 1 to 2 hours and the plasma half-life was shown to be approximately 12 hours. Adverse events were mostly mild to moderate in severity and principally included headache, nausea, vomiting, diarrhea, constipation, abdominal pain, dyspepsia, upper respiratory tract infection, lightheadedness, syncope, myalgia, dizziness, rash and pain at the lumbar puncture site in those subjects who had lumbar punctures. There was only one AE of severe intensity, being an SAE of upper respiratory tract infection, occurring in one subject in the 840 mg dose of the MAD study, believed to be unrelated to study drug based on a similar pattern of URTIs in subjects receiving drugs other than CT1812 in the study unit during the same time period. One subject in the multiple dose cohort study developed a rash while on study drug. This subject showed improvement after discontinuing CT1812.

No evidence of renal toxicity was observed based on routine measures of renal function (serum creatinine, BUN) or cystatin C.

Four subjects in the MAD study showed an increase in liver function tests below 3X the upper limit of normal (including one subject on placebo). Subsequent studies will closely monitor liver enzyme parameters to determine if these were sporadic findings or possibly drug related.

A fed cohort (280 mg) single dose was compared to the fasting cohort of 280 mg and no significant food effect was observed. A multiple dose cohort of elderly (≥ 65 years old) healthy volunteers was dosed at 560 mg x 14 days, and their exposures were similar to the 840 mg younger healthy volunteer subjects.

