Abbreviations: DLB = Dementia with Lewy Bodies, PROs= Patient Reported Outcomes, MoCA = Montreal Cognitive Assessment Scale, CAF= Clinician Assessment of Fluctuation, ESS = Epworth Sleepiness Scale, MDS-UPDRS part III = Movement Disorder Society – United Parkinson's Disease Rating Scale Part III, ADCS-CGIC = The Alzheimer's Disease Cooperative Study – Clinical Global Impression of Change, ADCS-ADL= The Alzheimer's Disease Cooperative Study - Activities of Daily Living, MMSE = Mini Mental State Exam, CDR= Cognitive Drug Research Battery, ApoE = apolipoprotein E, C-SSRS = Columbia Suicide Severity Rating Scale, ECG=electrocardiogram, GDS = Geriatric Depression Scale, PK=pharmacokinetic, NPI = Neuropsychiatric Inventory

1. Informed consent for subject and caregiver must be obtained prior to the subject undergoing any study-specific procedures.
2. Review of all criteria detailed in Sections 8.2 and 8.3
3. Record demographic information, confirm ethnicity and obtain medical history, drug and alcohol history, and education history.
4. Confirm DLB diagnosis in accordance with criteria based on the 4th report of the DLB Consortium (McKeith et al., 2017). See Appendix B.
5. Perform MMSE and GDS (see sections 11.1.8 and 11.1.7).
6. APOE genetic testing is required for all subjects (see section 9.2.1).
7. Screening labs include viral serology, TSH, FSH (for female subjects that are not surgically sterile) and HbA1c (for diabetic subjects only).
8. Complete physical examination = thorough examination of all body systems (including neurological exam), including height and weight. Weight should be measured on the same scale each time. Height measured only at screening (see section 12.1.2).
9. Brief physical examination = inquire about signs/symptoms, review of general appearance and brief review of body systems, including weight. Weight should be measured on the same scale each time (see section 12.1.2).
10. ECG to be conducted during screening period, and approximately one to two hours post-dose at specified visits (see section 12.1.7).
11. MRI (or CT scan due to contraindication of MRI if approved by medical monitor) performed at screen (if an historical MRI/CT scan is not used) (see section 12.1.8).
12. Vital Signs: body temperature, systolic and diastolic blood pressure, pulse rate and respiration rate
13. Safety labs – Blood Chemistry, Hematology and Urinalysis – Blood should be drawn within an hour of urine collection (see section 12.1.4).

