9.2 Visit Specific Procedures

9.2.1 Visit 1 / Screening

The Screening visit must be performed within 42 days prior to Day 1 – Baseline. The following procedures will be performed at the Screening visit:

- Subjects or their Legally Authorized Representative (LAR) (or designee as applicable by local law) must provide written informed consent to the study procedures prior to any study procedures. The caregiver must also provide written informed consent at this time.
- Evaluate subject eligibility against study inclusion/exclusion criteria.
- Confirm DLB diagnosis (see section Appendix B).
- Record demographic information, confirm ethnicity, alcohol and drug history, educational history and obtain medical history.
- Administer the Mini-Mental State Exam (MMSE) and Geriatric Depression Scale (GDS)
- Administer Modified Hoehn and Yahr
- Administer CAF and ESS
- Administer C-SSRS Screening/Baseline version
- Perform complete physical examination with neurological examination
- Measure and record vital signs
- Perform 12-lead ECG
- MRI (or CT scan due to contraindication of MRI, if approved by medical monitor), unless an historical MRI/CT scan is used.
- Draw blood and prepare samples for APOE status. Apolipoprotein E (ApoE) genotype is associated with the risk and age of onset of DLB. Blood samples (approximately 10 mL) to perform this testing will be collected and will be utilized to further understanding of response to CT1812. The genotyping is mandatory for participation in the study and the results will not be revealed to either the investigator or subject and caregiver.
- Draw blood and prepare samples for coagulation testing (PT/INR), serum chemistry, hematology, viral serology, TSH, FSH (in women who had their last natural menses less than 24 months prior to screening and who are not surgically sterile) and HbA1c (in known

diabetics), Blood should be drawn within an hour of urine collection. Abnormal results at screening will exclude a subject unless the investigator is aware of a specific reason that can explain the abnormality (e.g., elevated CPK 24 hours after strenuous exercise). Should an abnormal lab remain abnormal on repeat the subject will be excluded. Collect blood sample for exploratory biomarker samples

- Collect blood samples for exploratory plasma biomarker analysis
- Collect urine sample for β -HCG pregnancy test for women who are not postmenopausal (last natural menses was less than 24 months ago) that are not surgically sterile.

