9.2.2 Visit 2 / Study Day 1 – Baseline

The following procedures will be conducted on Day 1:

Pre-dose Assessments:

- Confirm continued eligibility prior to dosing.
- Administer MOCA, CDR, ADCS-ADL, NPI, ADCS-CGIC, MDS-UPDRS Part III, CAF and ESS
- Administer C-SSRS Since Last Visit version
- Perform complete physical examination with neurological examination
- Measure and record vital signs
- Draw blood and prepare sample for serum chemistry and hematology Blood should be drawn within an hour of urine collection.
- Collect whole blood sample for future biomedical research including potential genetic analyses
- Collect blood samples for PK and exploratory plasma biomarker analysis
- Collect urine samples for urinalysis
- Record any new medical conditions, AEs, or changes in medications since the Screening visit.
- Administer study drug with food.

Post-dose Assessments

- Record ECG ~1- 2 hours post-dose
- Dispense study drug supply and instructions for at home dosing.
- Instruct subject to return for Day 14 visit including instructions to bring study drug to the Day 14 visit

9.2.3 Visit 3 Study Day 14

The subject will return to the clinic for the following assessments:

- Measure and record vital signs
- Draw blood and prepare sample for serum chemistry and hematology. Blood should be drawn within an hour of urine collection.
- Collect urine samples for urinalysis,
- Record any AEs.
- Record changes in medications.
- Conduct drug accountability, return study drug to the subject for continued dosing
- Instruct subject to return for Day 28 visit including instructions to hold dose on morning of Day 28 visit and to bring study drug with them

9.2.4 Visit 4 Study Day 28

The subject will return to the clinic for the following assessments:

Pre-dose Assessments:

- Administer MOCA, CDR, ADCS-ADL, NPI, ADCS-CGIC, MDS-UPDRS Part III, CAF and ESS
- Administer C-SSRS Since Last Visit version
- Perform brief physical examination
- Measure and record vital signs
- Draw blood and prepare sample for serum chemistry and hematology.) Blood should be drawn within an hour of urine collection
- Collect blood samples for PK and exploratory plasma biomarker analysis

- Collect urine samples for urinalysis
- Record any AEs.
- Record changes in medications.
- Conduct drug accountability
- Collect remaining drug in old bottle.
- Administer Day 28 dose with food.

Post-dose Assessments:

- Record ECG ~1- 2 hours post -dose).

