14.4.2 Safety Analyses

Adverse events (AEs) will be assessed by the investigator for severity and will be coded for summarization using Medical Dictionary for Regulatory Activities (MedDRA® Version 24 or higher). The occurrence of AEs will be summarized by treatment using MedDRA system organ classification, preferred terms, and severity. Separate summaries of AEs, serious AEs, AEs related to study drug, and AEs leading to study discontinuation will be summarized by Preferred Term and System Organ Class.

Concomitant medications will be coded using WHO Drug Dictionary (enhanced) March 2021 or higher and summarized.

Laboratory measures will be summarized by treatment group and time-point both as absolute values and as change from baseline, with descriptive statistics summarizing each group and time point. Similar presentation will be used for vital signs and for ECG interval measurements, and changes from pre-treatment baseline.

Results from Columbia Suicide Severity Rating Scale (C-SSRS) will be listed.

Results from physical exam findings will be listed.

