## 15.6 Electrocardiogram

ECG parameters (ventricular rate, RR, PR, QRS, QT, QTcF and QTcB) will be summarized using descriptive statistics at baseline and at each post baseline time point. Changes from baseline will also be summarized. Interpretation results will present the number and percentage of normal, abnormal not clinically significant, and abnormal clinically significant results at each visit.

In addition, a categorical summary of abnormal corrected QT interval values will be presented. At each time point, the number of subjects with QTcF values of >450 ms, >480 ms, and >500 ms will be presented. At each postbaseline time point, the number of subjects with change from baseline values in QTcF of >30 ms and >60 ms will be presented.

Electrocardiogram results will be presented in a listing.

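### The SAP's date-based baseline rule makes the Day 1 ECG, taken 1–2 hours after the first dose, the ECG baseline, so an acute QTc effect is subtracted out of the ECG change summaries

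*SAP*

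**What the plan says.** SAP 10.2 gives the general rule: "baseline is defined as the last non missing value recorded before or on the date of first dose of study drug". Its only exception is for efficacy assessments, where a value up to 6 hours after the first dose may serve as baseline. SAP 15.6 adds no ECG-specific definition. It calls for mean changes in the ECG intervals and, at post-baseline time points, the number of subjects with "change from baseline values in QTcF of >30 ms and >60 ms will be presented".

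The protocol schedules ECGs at screening and on Days 1, 28, 98 and 182. At screening (9.2.1) the instruction is "Perform 12-lead ECG". On Day 1 (9.2.2) the ECG appears under the post-dose assessments: "Record ECG ~1- 2 hours post-dose". The key to Table 1 states the pattern for all visits: "ECG to be conducted during screening period, and approximately one to two hours post-dose at specified visits".

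Protocol 14.4.2 commits to summaries of "ECG interval measurements, and changes from pre-treatment baseline", and the synopsis says the same. SAP 16, which lists differences from the protocol, mentions only added analysis populations.

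**The concern.** Day 1 laboratory samples and vital signs are listed as pre-dose, so a date-based rule does no harm there. The ECG is different. Its only scheduled Day 1 recording follows the dose, so the last value on the date of first dose is an on-drug value. It replaces the screening ECG, the one scheduled drug-free tracing.

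Safety and tolerability are the primary objective. If the baseline already contains the drug effect, the mean ECG changes and the >30 and >60 ms QTcF counts would look reassuring whether or not CT1812 acutely prolongs QTc. The Day 1 recording also drops out of those counts, because it is no longer post-baseline. Protocol 3.2.3 reports two hERG assays with IC50 values of 26 and 0.6 in the same printed units and no explanation for the gap, so the ECG tables have a real question to answer.

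**Working it through.** The documents give no figure for the ECG baseline, so there is nothing to reproduce. The check traces the rule through the schedule and then sizes the consequence.

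**Step 1: which ECG the rule selects**

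| ECG | Timing | On or before date of first dose? | On drug? |
|---|---|---|---|
| Screening | Day -42 to -1 | Yes | No |
| Day 1 | 1–2 h post-dose | Yes, and the later of the two | Yes |
| Days 28, 98, 182 | 1–2 h post-dose | No | Yes |

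The rule takes the last qualifying value, so Day 1 becomes baseline. An unscheduled pre-dose ECG on Day 1 would not change this, because the post-dose one is still later on the same date. A subject with no Day 1 ECG falls back to screening, so the tables could mix on-drug and off-drug baselines.

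**Step 2: what the change then measures**

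Protocol 3.3 reports for the Phase 1a study: "Peak concentrations of CT1812 were reached within 1 to 2 hours and the plasma half-life was shown to be approximately 12 hours". It also describes accumulation as minimal. Let E be the first-dose QTc effect at 1–2 h and R the ratio of later peak exposure to first-dose peak exposure, with effect proportional to exposure.

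- Drug-free baseline: expected drug-related change = R × E.
- SAP rule: expected drug-related change = R × E − E = (R − 1) × E.

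With R = 1 the SAP rule gives 0. Taking the 12 h half-life and 24 h dosing at face value, R = 1/(1 − 0.5^(24/12)) = 1.33. The SAP rule then keeps 0.33E out of 1.33E, or 25% of the steady-state effect. For assumed half-lives of 8 to 16 h the share kept is 12.5% to 35%. The first-dose effect E is removed in full in every case. Placebo has no drug effect at either time, so the active-minus-placebo difference in change loses the same amount.

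**Step 3: effect on the >30 ms count**

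P(change > 30 ms) = 1 − Φ((30 − m)/SD), where m is the expected change. The documents give neither a QTc effect nor an SD, so both are assumed. With R = 1:

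| Assumed SD | Assumed E | Drug-free baseline (m = E) | SAP rule (m = 0) |
|---|---|---|---|
| 14 ms | 10 ms | 7.7% | 1.6% |
| 14 ms | 15 ms | 14.2% | 1.6% |
| 14 ms | 20 ms | 23.8% | 1.6% |
| 10 ms | 10 ms | 2.3% | 0.1% |
| 10 ms | 15 ms | 6.7% | 0.1% |
| 10 ms | 20 ms | 15.9% | 0.1% |

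For example, with SD 14 and E = 10: (30 − 10)/14 = 1.43, and the upper tail is 7.7%. The last column is simply the no-effect rate, so it does not vary with E.

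In an arm of 40, over E of 5–20 ms and SD of 10–20 ms, the expected count runs from 0.25 to 12.3 with a drug-free baseline and from 0.05 to 2.7 under the SAP rule.

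Allowing for accumulation (R = 1.33, E = 10 ms, SD = 15 ms), m is 13.3 ms against 3.3 ms. The proportions are 13.3% against 3.8%, or 5.3 against 1.5 subjects of 40. Most of the signal is still lost.

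**The case against.** The strongest reply is that the plan is not blind to QTc. SAP 15.6 also summarises observed ECG values, counts QTcF above 450, 480 and 500 ms, and tabulates normal and abnormal readings by visit. None of these uses a baseline, and there is a randomised placebo arm. A sizeable acute effect could appear there, including on Day 1. This stands, and it limits the damage to the change-based summaries.

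Full cancellation also depends on similar peak exposure on Day 1 and later. The accumulation statement comes from healthy volunteers, and Protocol 3.3 notes that an elderly cohort on 560 mg had exposures like younger subjects on 840 mg. Kinetics at ages 50–85 may therefore differ, and an effect that builds after the first dose would partly survive. This also stands, although the first-dose component is always lost.

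The percentages rest on assumed effects and on one SD for both baselines. A screening ECG up to 42 days old and not matched for time of day may give a larger SD of change. That would raise the outlier rate in every arm, placebo included, so the counts should be read against placebo. It does not justify an on-drug baseline.

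The hERG discordance needs balance: the same section reports no ECG effects in two dog studies, up to mean peak levels of about 4 µM. That lowers prior concern but does not excuse a summary that cannot detect an acute effect.

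Finally, one could argue that the rule obviously means pre-dose, and that this is a slip of date for time. That may be the intent. The text does not say it, though, and the next sentence of SAP 10.2 accepts efficacy baselines after dosing, so a programmer cannot infer a pre-dose limit.

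**Conclusion.** The concern holds. As written, the SAP makes an on-drug ECG near peak concentration the baseline, contradicts the protocol's pre-treatment baseline and does not declare the change. For ECG, the mean changes from baseline and the >30 and >60 ms QTcF counts lose the whole first-dose effect. That is essentially all of an acute effect if peak exposure is similar on Day 1 and later, and about three quarters of the steady-state effect if accumulation follows a 12 h half-life. The outlier percentages illustrate scale only, since the effect sizes and SDs are assumed. Other safety variables, the observed ECG values and the absolute QTcF categories are not affected. Because safety is the primary objective and the correction is simple, it should be made before the blind is broken; SAP 6 treats anything later as post hoc.

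**What to change.** In SAP 10.2 and 15.6, define the ECG baseline as the last non-missing ECG recorded before the date and time of first dose. Under the current schedule that is the screening ECG, or an unscheduled pre-dose ECG if one exists. Present the Day 1 recording at 1–2 h as the first post-baseline time point, with its own mean change and its own >30 and >60 ms counts. Label it so that the Day 1 visit name, Baseline in the SAP's visit table, is not read as the ECG baseline.

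A date-and-time cut-off in the general rule for all safety parameters would be sound practice. It is not needed for laboratory tests and vital signs if they are collected pre-dose as scheduled.

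The cost is a few lines of SAP text and one derivation in the ECG dataset, with no new data. The downside is a baseline that can be up to 42 days old and is not matched for time of day. This applies to all arms alike, so change should be interpreted against placebo.
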